The desire for minimally invasive safe and less traumatic cellulite treatments has grown substantially in recent years. Minimally invasive, temperature-controlled radiofrequency (RF)-based technology offers an optimal energy-based alternative.

Radiofrequency-assisted lipolysis (RFAL) technology was introduced by InMode Ltd., Israel about 10 years ago. RF energy is applied to the treatment area using a handpiece with 2 electrodes. An internal active electrode emitting coagulative thermal energy targets the deep soft tissues, as well as releases tissue in dimples by cutting fibrous septa with spatula-shaped tip.

The external electrode is larger compared to the internal electrode, thus having relatively low energy density that creates nonablative RF heating. RF flows between the internal and the external electrode placed on the skin, heating the tissue in between the electrodes and causing a thermo coagulative effect. The treatment stimulates contraction and collagen formation and simultaneously coagulates and liquifies adipose tissue with profound contraction of the fibroseptal network (FSN)¹⁻⁴. The RFAL technology became a well-established alternative for body^{3,4}, face and neck^{2,5-7} rejuvenation treatments using RFAL based handpieces.

[figure not shown]
InMode RF technology with a few handpieces was cleared by the FDA for electro-coagulation and hemostasis (K171593, K163190, K151793).

The InMode system with the Morpheus8 Handpiece (K180189) is designed for delivering RF energy to the skin surface in a fractional manner. The energy is delivered to the skin through bipolar arrays of 24 insulated pins and results in localized heating and ablation of the skin that is in direct contact with the pins non-insulated tip. Ablation of the skin promotes skin renewal while untreated skin between the pins enables faster healing of the tissue. There is also the contribution of non-ablative, non-coagulating dermal matrix heating that occurs in the skin that is not subject to fractional ablation.

This prospective study is intended to evaluate the safety and efficacy of a new CelluTite RFAL handpiece combined with Morpheus8 handpiece for the treatment of cellulite.

3. Definitions, Acronyms and Abbreviations

RF - Radiofrequency

RFAL - Radiofrequency-assisted lipolysis

AE - Adverse Events

SAEs - Serious Adverse Events

UADEs - Unanticipated Adverse Device Effects

HP - Handpiece

4. Device Description

[figure not shown]
The InMode RF™ System is employing radiofrequency (RF) energy for use in dermatological and general surgical procedures for electrocoagulation and hemostasis. The System operates when Handpiece is connected.

The InModeRF System with CelluTite HP provides individual adjustment of treatment parameters to achieve maximum efficiency and safety for the specific treatment. The System provides enhanced safety while minimizing possible side effects by monitoring RF parameters and tissue temperature.

The System incorporates the following safety features. All personnel operating the System should be familiar with these features.

- System has unique password to avoid device operation by non-authorized personnel.
- The RF energy cannot be activated unless the applicator and footswitch have been connected to the System.
- An audible tone indicates energy activation.
- During activation, the System performs a self-test of the hardware.
- Hardware is tested every 10ms to ensure proper operation of electrical circuit.
- Tissue impedance monitoring prevents accidental energy emission to the patient.
- Skin surface is monitored during the treatment. RF energy delivery is terminated when skin temperature accidentally reaches the Cut-off level.
- System starts at a low setting.
- Internal and skin surface temperature and impedance are constantly monitored.

The InMode System with the Morpheus8 HP is designed to deliver radiofrequency energy to the skin in a non-homogeneous fractional manner, via an array of 24-electrode pins. The array delivers bipolar RF energy to the skin, resulting in heating of skin around the electrodes contact, to temperatures leading to electrocoagulation and homeostasis of small portions of the skin. The procedure is carried out while leaving untouched areas in-between the pin electrodes. This

maintains the integrity of the treated skin and serves as a reservoir of cells that accelerate and promote the healing process.

The System provides individual adjustment of treatment parameters to achieve maximum efficiency and safety for each patient and applications.

The Morpheus8 HP contains the following safety features:

- System has a password to avoid device operation by non-authorized personnel.
- The power electronics cannot be activated unless the applicator and footswitch have been connected to the System.
- An audible tone indicates energy activation.
- During activation, the system performs a self-test of the hardware.
- Hardware is tested every 10ms to ensure proper operation of electrical circuit.
- System starts at a low setting.

5. Study Objectives

The objective of this clinical study is to evaluate the safety and efficacy of treatment with CelluTite RFAL HP and Morpheus8 HP.

6. Study Endpoints

6.1 Efficacy Endpoints

Photographs evaluation: Photographs should always be taken under the same settings, including distance, angle, background, lighting and body position. Angles to include front, back and side views (90º angles and 30º angles).

Photos from all time points (baseline before treatment and at follow-up visits) will be evaluated by the treating physician and 2 independent evaluators.

Optional: Photos will be taken using QuantifiCare (imaging specializing in skin evaluations in clinical trials) at baseline and 6M FU visit

Clinician Reported Photonumeric Cellulite Severity Scale (CR-PCSS)⁸: This 5-point photonumeric scale rates cellulite severity from "0" (none) to "4" (severe) from a clinician's perspective in two main clinical morphologic features of cellulite (categories): (A) number of evident dimples (Figure 1); and (B) severity of linear undulations (contour irregularities) (Figure 2).

[figure not shown]

Table 1. Cellulite Severity Scale

	0	1	2	3	4
Number of evident dimples	(A) None/no dimples	(B) 1 dimple	(C)2 dimples	(D) 3 dimples	(E) 4 or more dimples
Severity of linear undulations (contour irregularities)	(A) None—no depressions or raised areas	(B) superficial: generalized, small depressions with no protuberances;	(C) mild: pattern of mild linear undulations with alternating areas of protuberances and depressions	(D) moderate: pattern of moderate linear undulations with alternating areas of protuberances and depressions	(E) severe: severe generalized linear undulations with alternating areas of protuberances and depressions

[figure not shown]
[figure not shown]

Figure 1. Number of evident dimples

[figure not shown]

Figure 2. Severity of linear undulations (contour irregularities)

[figure not shown]

6.2 Safety Endpoint

Observation, assessment and recording of adverse events. Evaluations will be done immediately after treatment and at all follow-up visits. The frequency, severity and causality of all adverse events will be recorded.

Possible CelluTite adverse effects include but are not limited by:

- Discomfort or pain
- Excessive skin redness (erythema)

- Excessive skin swelling (edema)
- Ecchymosis
- Damage to natural skin texture (crust, blister, burn)
- Change of pigmentation (hyper- and hypo-pigmentation)
- Scarring
- Very slight risk of infection
- Incision port scarring
- Surface Irregularity
- Numbness
- Seroma
- Side effects related to anesthesia

Possible Morpheus8 adverse effects include but are not limited by:

- Discomfort or pain
- Excessive skin redness (erythema)
- Excessive skin swelling (edema)
- Damage to natural skin texture (crust, blister, burn)
- Change of pigmentation (hyper- and hypo-pigmentation)
- Localized infection
- Scarring

Erythema lasting not longer than 24h and edema for 1-3 weeks is a typical skin reaction to the Morpheus8 treatment.

Crusting from the ablated dots will exfoliate naturally after 1-3 weeks.

Adverse events will be classified as Mild, Moderate, and Severe. The duration of the adverse event until it subsides will also be recorded.

7. Study Population

[figure not shown]
7.1 General Considerations

The study will recruit approximately 70 female subjects, between the ages of 18-70, having small body areas with adipose tissue, seeking cellulite treatments.

Treatment areas include Exterior (Lateral) and posterior thighs

Optional: Buttocks treated with Morpheus Applicator only

Eligible subjects will be screened. Investigators will screen subjects based on the inclusion/exclusion criteria described below after a written informed consent is signed.

7.2 Inclusion Criteria

- Female subjects aged 18-70 having mild/moderate grade cellulites.
- The patients should understand the information provided about the treatment, possible benefits and side effects, and sign the Informed Consent Form, (including the permission to use photography).
- The patients should be willing to comply with the study procedure and schedule, including the follow up visit, and will refrain from using any other aesthetic treatment methods in the treatment area for the last 6 months and during the entire study period.

7.3 Exclusion criteria

- Body fat layer thinner than 5mm.
- Pacemaker or internal defibrillator, or any other active electrical implant anywhere in the body.
- Superficial permanent implant in the treated area such as metal plates and screws, metal piercing, silicone implants or an injected chemical substance.
- Current or history of skin cancer (remission of 5 years), or current condition of any other type of cancer, or pre-malignant moles.
- Severe concurrent conditions, such as cardiac disorders, epilepsy, uncontrolled hypertension, and liver or kidney diseases.
- Pregnancy and nursing.
- History of bleeding coagulopathies or use of anticoagulants.
- Impaired immune system due to immunosuppressive diseases such as AIDS and HIV or use of immunosuppressive medications.
- Poorly controlled endocrine disorders, such as diabetes or thyroid dysfunction and hormonal virilization.
- Any active condition in the treatment area, such as sores, psoriasis, eczema, and rash.
- History of skin disorders, keloids, abnormal wound healing, as well as very dry and fragile skin.
- Use of Isotretinoin (Accutane®) within 6 months prior to treatment.
- Any surgery or treatment such as laser or chemicals in treated area within 3-6 months prior to treatment or before complete healing.
- Allergies, in particular to anesthesia.
- Mental disorders such as Body Dysmorphic Disorder (BDD).
- As per the practitioner's discretion, refrain from treating any condition that might make it unsafe for the patient.

8. Study Design

The study is a prospective, open label clinical study.

Approximately 70 subjects will be recruited for the study.

Clinical Evaluation of Safety and Efficacy of The CelluTite Treatment		
Protocol No:	DO608110C	Rev. Date: August 15, 2019
IRB ID:	7030	

Treatment areas include Exterior (Lateral) and posterior thighs

Optional: Buttocks treated with Morpheus Applicator only

The treatment will be conducted according to the guidelines in the operator manual.

The treatment efficacy will be evaluated by comparing 1, 3 and 6 months follow-up photos and cellulite grade to baseline.

Each subject will undergo 5-6 study visits including screening, treatment and 4 follow-up visits.

The Time and Events Schedule is provided in Appendix I.

8.1 Screening and Baseline (Visit 1)

Screening visit will be performed in order to determine subject eligibility and to collect all required demographic and baseline clinical information. Study procedures and available treatment options, including the CelluTite RFAL and Fractional RF technology will be described in detail to the subject. Subject will be assured that the decision regarding participation in the study is strictly voluntary and that they are free to change their mind at any stage. Subjects who decide to participate in the study will sign the Informed Consent form and Photo Release form prior to any study related procedure.

Subjects will then be screened for study eligibility according to inclusion and exclusion criteria.

The following Demographic and Baseline Measurements will be performed:

- Demographic data including gender, age, race, skin type (Fitzpatrick scale).
- Medical history and concomitant medication usage.
- Baseline photos and assessments will be taken.

8.2 Treatment

The CelluTite HP treatment may occur on the same day of screening and baseline visit (or within 3 weeks following screening).

Treatment area: Treatment areas include exterior (lateral) and posterior thighs Optional: Buttocks treated with Morpheus Applicator only

Treatment procedure

[figure not shown]
- Treatment will be conducted according to instructions in the operator manual and company guidelines.

	Clinical Evalua	Clinical Evaluation of Safety and Efficacy of The CelluTite Treatment			
INMODE	Protocol No:	DO608110C	Rev. Date: August 15, 2019		
	IRB ID:	7030			
aesthetic solutions					

- Local anesthesia should be injected, incisions should be created for tumescent and internal electrode insertion and tumescent anesthesia should be applied. Make two or three incisions for each side. One on the low side of the thigh and 1 or 2 on the top area.
- Sterile water—based gel, such as ultrasound gel should be applied to the skin surface to insure good contact of external electrode.
- Insert CelluTite cannula to the most distal protrusion.
- Treat protrusion area to reach internal cut off. Treat depressed areas without energy to mechanically release septa and elevate the dimples.
- Treat only in one plane at the depth of 7-20mm depending on fat thickness and severity of cellulite.
- Use 40°C external cut-off and 60°C internal cut-off. Higher setting (40°C/70°C) can be used for depth 15-20mm.
- Cannula should be inserted to the intended tissue and good contact of return electrode with skin surface should be ensured.
- While RF is applied, footswitch should be pressed.
- Treat all dimples/depressions in the treatment area.
- Treat all marked areas uniformly.
- After RFAL heating, no or minimal aspiration is recommended. Aspiration is performed with slow cannula movement to take liquified fat out without additional mechanical destruction of tissue. However, aggressive external "milking" of melted fat out of the treatment zone should be performed through the incision port to reduce risk of seroma and level of inflammation. Even pressure should be applied when milking the treatment area to achieve outcomes that are uniform in contour.
- Endpoint of the CelluTite treatment is achievement of temperature cut-off.
- Set Morpheus8 hand piece with BODY treatment depth and energy level of 40 in Fixed mode and double stack with 2 consecutive pulses on the same spot. Apply 2 passes of Morpheus8 with 50% overlap to all treated area.

If subject has grade III cellulite and dimples are present:

- .1 Step 1: Release bands/dimples with the CelluTite handpiece exercising caution not to reach maximum cutoff temperature.
- Step 2: Set Morpheus8 hand piece with BODY treatment depth and energy level of 40 in Fixed mode and double stack with 2 consecutive pulses on the same spot. Apply 2 passes of Morpheus8 with 50% overlap to all treated area. Step 3: Harvest Fat and Fat Transfer additional procedure called fat grafting and/or EVL (Expansion Vibration Lipofilling) might be performed to further expand and even the area of concern. During this procedure the physician will remove unwanted fat from a "donor" zone and add it to another zone of the thigh. If subjects meet the criteria for this procedure it will be discussed during the screening.
- Loose closing of the incision port with a suture provides drainage of treated area after the treatment.
- Compressing garments must be applied at least for 1-2 weeks following the treatment.

 Optional: Apply topical anesthesia on Buttocks area and treat with Morpheus Applicator only. Set Morpheus8 hand piece with BODY treatment depth and energy level of 40 in Fixed mode and double stack with 2 consecutive pulses on the same spot. Apply 2 passes of Morpheus8 with 50% overlap to all treated area.

After treatment, observation, assessment and recording of adverse events will be conducted.

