Cover Letter:

Enclosed bellow documents are part of the Clinical Trial NCT03769649

Study Name: Clinical Evaluation of Safety and

Efficacy of The CelluTite Treatment

Revision Date: August 15, 2019

Clinical Evaluation of Safety an	l Efficacy of The C	ElluTite Treatment
----------------------------------	---------------------	--------------------

IRB ID: 7030

Rev. Date: August 15, 2019

Study Name: Clinical Evaluation of Safety and Efficacy of The

CelluTite Treatment

Protocol No.: DO608110

Revision No.: 4

Sponsor: InMode MD Ltd.

[name]

[name]

[name]

[name]

[contact]

[contact]

	Clinical Evaluation	on of Safety and Efficac	y of The CelluTite Treatment
	Protocol No:	DO608110C	Rev. Date: August 15, 2019
•	IRB ID:	7030	

Clinical Evaluation of	Safety	and Efficacy o	of The Cell	ˈuTite Treatment

IRB ID: 7030

Rev. Date: August 15, 2019

1. Protocol Synopsis

Study Title	Evaluation of Safety and Efficacy of The CelluTite Treatment
Protocol No	DO608110C
Sponsor	InMode MD Ltd.
Device	InMode RF system CelluTite RFAL hand piece HP172248.
	Morpheus8 Applicator
Study Design	Prospective single centre, open label clinical study.
Study Objectives	The aim of the study is to evaluate the safety and efficacy of cellulite treatment with HP172248 and Morpheus8.
Study Sites	[name], [name]
Patient Population and Sample Size	Approximately 10 female subjects , aged 18-70 having grade II and mild/moderate grade III cellulites.
Treatment areas	Exterior (lateral) and posterior thighs
	Optional: Buttocks with Morpheus Applicator only
Study Duration	Study duration for each subject is approximately seven months (including screening, one treatment and four follow-up visits at 1 week, 1 month, 3 months and 6 months post treatment.
	Overall study duration will be approximately 12 months, depending on the subject recruitment rate.
Efficacy Endpoints	Photographs evaluation: Photos from all time points (baseline and follow-up visits) will be evaluated by the treating physician and 2 blinded independent evaluators.
	Optional: Photos will be taken using QuantifiCare (imaging specializing in skin evaluations in clinical trials) at baseline and 6M FU visit.
	Evaluation goals are rating the degree of cellulite according to Clinician Reported Photonumeric Cellulite Severity Scale (CR-PCSS).

Clinical Evalua	tion of Safety and Eff	icacy of The CelluTite Treatment	

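### Optional fat grafting in grade III thighs is pooled with device-only subjects, so the mean change credited to CelluTite and Morpheus8 could be shifted by (share grafted) × (graft effect)

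*Combined protocol and SAP*

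**What the plan says.** Section 5 sets the aim: to "evaluate the safety and efficacy of treatment with CelluTite RFAL HP and Morpheus8 HP". Fat transfer is not mentioned there.

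Section 8.2 gives a general procedure and then a variant for subjects with grade III cellulite and dimples. Step 3 of the variant says that "fat grafting and/or EVL (Expansion Vibration Lipofilling) might be performed to further expand and even the area of concern". Fat is taken from a donor zone and placed in another zone of the thigh. On selection, the section says only: "If subjects meet the criteria for this procedure it will be discussed during the screening". No criteria beyond grade III with dimples are given. The synopsis includes grade III in the target population.

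The CelluTite step also differs between the two procedures. In general, "Endpoint of the CelluTite treatment is achievement of temperature cut-off"; in the grade III variant the operator releases bands and dimples while "exercising caution not to reach maximum cutoff temperature".

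Section 6.1 scores efficacy on CR-PCSS, 0 to 4, in two categories: number of dimples and severity of contour undulation. Section 16.1 defines one performance set, all subjects with at least one post-treatment measurement. Section 16.2 plans means, SDs and a paired t-test at two-sided 0.05. Neither section mentions grafting.

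Section 14.2 provides a Treatment Visit Form that captures details of the procedure.

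**The concern.** Grafting is meant to even out the thigh surface, and the efficacy scale measures dimples and unevenness. That the grafted zone is the scored zone is the natural reading, although the text does not say so outright. With a single arm, no comparison group receives the same grafting and cancels its contribution. Any change due to transferred fat goes into the same mean as change due to the handpieces, and the planned test does not separate them.

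What is at stake is attribution. A favourable result could be credited to the devices when part of it comes from grafting. If grafting worsens contour, a real device effect could be understated. Safety, the other half of the objective, has the same problem: donor-site and graft events would be mixed with device events.

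**Working it through.** The plan states no effect size, SD or power, so there is no figure of its own to reproduce.

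**Identity.** Count improvement as positive. Let D be the mean change from the devices, s the share grafted, and G the mean extra change among those grafted. Then

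expected pooled change = D + s × G.

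The documents give neither s nor G. If s = 0 the shift is 0, and its sign is the sign of G.

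**Inputs from the documents.** Paired t-test, two-sided 0.05, hence 2.5% in the favourable direction (16.2). About 70 subjects (7.1 and 8), but the synopsis has "Approximately 10 female subjects", so both sizes are used.

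**Assumed inputs.** s = 0.10; G = 0.5 to 2 CR-PCSS points; SD of change 0.8 or 1.0 point. The shift is then 0.10 × 0.5 = 0.05 up to 0.10 × 2 = 0.20 point.

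**Falsely favourable rate with D = 0** (simulation, 20,000 runs per cell; change = Normal(0, SD) + G × Bernoulli(0.1)):

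| n | SD | G = 0.5 | G = 1 | G = 1.5 | G = 2 |
|---|---|---|---|---|---|
| 70 | 0.8 | 0.070 | 0.155 | 0.263 | 0.370 |
| 70 | 1.0 | 0.059 | 0.118 | 0.198 | 0.281 |
| 10 | 0.8 | 0.036 | 0.048 | 0.056 | 0.055 |
| 10 | 1.0 | 0.034 | 0.045 | 0.053 | 0.056 |

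With nobody grafted the rate is 0.022–0.026.

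**Opposite sign.** Take n = 70, D = 0.3, G = −0.5 and s = 0.10. The shift is −0.05 point. Power falls from 0.872 to 0.714 (SD 0.8) and from 0.697 to 0.532 (SD 1.0).

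**Why not simply drop whoever was grafted?** Step 3 is worded as optional, so the decision could follow how the thigh looks after Steps 1 and 2. Suppose D = 0, n = 70, the worst-looking 30% are grafted, and that appearance correlates 0.2, 0.3 or 0.5 with the final change. Keeping only ungrafted subjects then gives falsely favourable rates of about 0.10, 0.18 and 0.44. With 10% grafted they are about 0.05, 0.07 and 0.12. A set fixed before treatment gives 0.023–0.027, but only because designation was assumed independent of the later result.

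**Price of a device-only set** (noncentral t, true change 0.3 point, starting from 70):

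| Designated | n left | Power, SD 0.8 | Power, SD 1.0 |
|---|---|---|---|
| 0% | 70 | 0.872 | 0.697 |
| 10% | 63 | 0.834 | 0.650 |
| 30% | 49 | 0.730 | 0.539 |

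The 10% row uses the same share as the harm illustration and is the one to set against it.

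**The case against.** The strongest reply is that grafting belongs to the regimen. Step 3 sits inside the treatment section, grade III subjects are in the target population, and an analysis of treatment as delivered is legitimate. This stands to a degree: the all-subjects result should be kept, and removing the more severe subjects from the main conclusion would be a choice with its own cost. It does not license a statement about two handpieces alone, because the objective names only those and the protocol itself treats grafting as something added.

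A second reply is that the size is wholly assumed. That also stands. The 37% is an extreme corner (no device effect, a 2-point graft effect on a 0-to-4 scale, SD 0.8, n = 70). With 2% grafted at n = 70 the rate is only 3–5%, and at n = 10 it is near nominal throughout.

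Three stronger readings are tempting, and the documents do not support them:

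- *The estimate is inflated.* Grafting is optional, its frequency is unknown, and its effect could go either way.
- *The report could never show who was grafted.* The Treatment Visit Form records details of the procedure, so grafts could probably be identified. What is missing is an analysis that uses the information.
- *Fixing the set before treatment restores the 2.5% rate.* Candidacy depends on grade III with dimples, so it may correlate with change. A correlation of 0.2 in the unfavourable direction would give the same rate of about 0.10 as dropping grafted subjects; in the other direction the rate falls below 2.5%.

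Nor do the documents say that grafting is decided after Steps 1 and 2. They place a discussion at screening; they do not require the decision to be made or recorded then.

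**Conclusion.** The concern holds as a conditional bias in a stated analysis. Followed as written, the plan can credit graft effects to the devices, by exactly s × G. That structure follows from sections 5, 8.2, 16.1 and 16.2, together with the natural reading that the grafted zone is scored.

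The size cannot be determined from the documents. Under the assumed inputs above, the falsely favourable rate is about 6–37% at 70 subjects and about 3–6% at 10; with a graft that harms, power is lost instead. It should be fixed, because the remedy is cheap and a split chosen after results are seen would not be prespecified.

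**What to change.** **Sections 8.1 and 8.2.** State the graft criteria. Record candidacy (planned yes/no, side, zone) at screening and before Step 1. The order needs stating because "The CelluTite HP treatment may occur on the same day of screening and baseline visit". Flag graft/EVL done (yes/no, side, zone) on the existing Treatment Visit Form.

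**Sections 16.1 and 16.2.** Prespecify two results side by side:

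1. all subjects, labelled as the regimen delivered, including any grafting;
2. subjects not designated for grafting.

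Rest any statement about the two devices alone on the second. Report the number grafted. List grafts that depart from the designation, and show the second result with and without those subjects. Tabulate adverse events by graft status.

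Do not define the device set by whether grafting was done. Do not read the difference between designated and other subjects as the graft effect, because grade and CelluTite technique differ too.

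**Cost.** One screening field, one flag, some wording, and possibly an amendment needing IRB approval. The device-only set is smaller and less severe: power for 0.3 point goes from 70–87% to 65–83% if 10% are designated, or to 54–73% if 30% are. Its result applies to non-designated subjects only, and the change does not make up for the lack of a control group.
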